### 14.2 Secondary Endpoints

- Change from baseline in the levels of infectious viral units per million CD4 T cells (IUPM) as determined by viral outgrowth assays and TILDA assays after study completion.
- Change from baseline in histone H3 acetylation in CD4 T cells during treatment with the study medication, as determined by changes in the acetylated H3 mean fluorescence intensity determined by flow cytometry.
- Change from baseline in levels of CD4 T cell-associated HIV-1 RNA during treatment with study medication, determined by qRT-PCR.
- Change from baseline in levels of plasma HIV-1 RNA during treatment with study medication, determined by single-copy assay or standard HIV-1 plasma assays.
- Change from baseline in levels of CD4 T cell-associated HIV-1 2-LTR circles and chromosomally integrated proviral HIV-1 DNA during treatment with study medication.
- Change from baseline in levels of HIV-1 DNA in different CD4 T cell subsets (naïve, T memory stem cells, central-memory, effector-memory, terminally-differentiated) during treatment with study medication.
- Change from baseline in frequency and function of innate and adaptive immune effector cell responses during treatment with study medication, as determined using phenotypic and functional immunologic assays.
- Change from baseline in levels of cellular and soluble immune activation markers during treatment with study medication, as determined by ELISA assays, luminex assays and flow cytometry.
- Change from baseline in expression patterns of interferon-stimulated genes (ISG) during treatment with study medication.
- Comparison of all immunological and virological parameters in study participants treated with IFN- $\alpha$  and panobinostat stratified according to HLA class I and IL-28B genotypes.

### 14.3 Sample Size Considerations

The primary efficacy analysis will compare changes from baseline to post-treatment HIV-1 DNA changes between the randomized treatment arms in stage 3. Allowing for one unevaluable participant in each arm due to lost to follow-up, ART discontinuation and/or other reasons, and under the assumption that a common standard deviation of change (measured as difference of log10 transformed HIV-1 DNA copies/million CD4 T cells) in all treatment arms is 0.436 (derived from baseline to end-of-study change in

## Protocol

the CLEAR study), the study with N=18 participants (9 evaluable participants treated with panobinostat and PEG-IFN- $\alpha$ 2a and 3 each treated with panobinostat or PEG-IFN- $\alpha$ 2a alone) will have 80% power to detect an effect size of 0.82  $\log_{10}$  (6.6-fold) in change of proviral CD4 T cell-associated HIV DNA level from baseline to day 10 in participants treated with panobinostat and PEG-IFN- $\alpha$ 2a compared to participants treated with panobinostat or PEG-IFN- $\alpha$ 2a only using a one-sided Wilcoxon rank sum test on a level of  $\alpha=0.05$ , assuming a normal distribution. The above power estimation does not take into account of multiple comparisons for this pilot study.

True Probability	N =8	N =8
	Probability of at least 1 event	Probability of at least 2 events
0.01	0.08	0.00
0.05	0.34	0.06
0.10	0.57	0.19
0.12	0.64	0.25
0.15	0.73	0.34
0.20	0.83	0.50

**Table 7:** Probability of safety endpoints in stage 1 and 2.

Regarding the assessment of safety, Table 7 and Table 8 display the probability of observing at least one or two participants with primary safety event with n=8 and 18 receiving study treatment. If the true probability is 10%, the study will have >57% probability of observing at least one participant with primary safety event in Stage 1 and 2 with 8 participants. The probability will be 85% for Stage 3 with N=18 participants.

True Probability	N =18	N =18
	Probability of at least 1 event	Probability of at least 2 events
0.01	0.17	0.01
0.05	0.60	0.23
0.10	0.85	0.55
0.12	0.90	0.65
0.15	0.95	0.78
0.20	0.98	0.90

**Table 8:** Probability of safety endpoints in stage 3.

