### 14.4.3 Statistical analysis of virological and immunological data

The primary efficacy endpoint is the change from baseline to day 10 in the number of HIV-1 infected CD4 T cells, as assessed by proviral CD4 T cell-associated HIV-1 DNA levels determined on a log-scale. The null hypothesis of no difference in the primary efficacy endpoint between the randomized treatments will be tested using a one-sided Wilcoxon rank sum test. The null hypothesis will be rejected with a  $p < 0.05$ .

Changes in the frequency of HIV-1-infected CD4 T cells (determined by levels of CD4 T cell-associated proviral HIV-1 DNA) from baseline to completion of the treatment phase will also be summarized as secondary efficacy endpoints and compared between the two randomized treatments. Mean and quartile plots will be used to summarize these efficacy endpoints at each visit. If feasible with the modest sample size, longitudinal data methods will also be used to evaluate and estimate treatment effects.

Analysis for the primary efficacy endpoint will use a modified intent-to-treat analysis, limiting to participants who have received at least one dose of randomized treatment and have data at baseline and day 10. Participants who go off ART, experience virologic failure or discontinue study participation for other reasons will be excluded from the efficacy analysis. For this analysis, mixed models with repeated measures will be considered (MMRM). Missing data will be managed using guidelines defined by the National Research Council.

Primary safety endpoints will be tabulated by Cohorts and randomized treatments.

Analyses of secondary virologic and immunologic outcomes will parallel the primary analyses outline above.

Baseline immunologic and virologic parameters will be assessed at multiple pre-entry timepoints (see Table 1). For analysis of primary and secondary endpoints, the mean of multiple baseline assessments will be used.

Secondary analyses of all immunologic and virologic parameters stratified by genetic polymorphisms (in HLA and IL-28B genes) will also be carried out.

Associations between changes in the various virologic and immunologic measurements will be evaluated using scatterplots and correlation coefficients.

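### Does the p < 0.05 rule in section 14.4.3 undercut the 80% power that section 14.3 states for 9 versus 3 participants?

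*Combined protocol and SAP*

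**What the plan says.** Section 14.3 (Sample Size Considerations) bases the stage 3 power on evaluable numbers after losses: "Allowing for one unevaluable participant in each arm", which takes the randomised 10, 4 and 4 of section 7.5 down to "9 evaluable participants treated with panobinostat and PEG-IFN"-α2a "and 3 each treated with panobinostat or PEG-IFN"-α2a alone. The common standard deviation of the log10 change "is 0.436 (derived from baseline to end-of-study change in" the CLEAR study. On these inputs the study "will have 80% power to detect an effect size of 0.82" log10 (6.6-fold), "using a one-sided Wilcoxon rank sum test on a level of" 0.05, with normally distributed changes. The same paragraph says that the power figure makes no allowance for multiple comparisons.

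Section 14.4.3 says that the null hypothesis for the change to day 10 "will be tested using a one-sided Wilcoxon rank sum test". It then gives the decision rule: "The null hypothesis will be rejected with a $p < 0.05". Neither section says whether the p-value comes from the exact permutation distribution or from a normal approximation.

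**The concern.** With three participants in a comparator arm the rank sum statistic takes few values, and many analysts would use the exact test. At 9 versus 3 the exact one-sided p-value for one result falls on 0.05 exactly. A test at level 0.05 may include that result in its rejection region. A rule of p strictly below 0.05 excludes it. Read that way, section 14.4.3 describes a more conservative test than the one behind the 80% in section 14.3, and the two sections seem to disagree.

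Two things would be at stake. The stated power would be about 8 percentage points too high for the planned evaluable numbers. And for one particular result the primary efficacy conclusion would depend on a p-value method that the plan leaves open, in an open-label trial where the choice could be made after the data are seen.

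**Working it through.** **Inputs.** From section 14.3: difference 0.82 log10, SD 0.436, 9 versus 3 evaluable, one-sided level 0.05, normal distribution. From section 14.4.3: one-sided Wilcoxon rank sum test, reject at p < 0.05. From section 7.5: 10 versus 4 randomised. No ties are assumed.

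**Statistic.** Let U be the number of (single-agent, combination) pairs in which the single-agent participant has the lower change. There are 3 × 9 = 27 pairs, and a small U favours the combination.

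**Exact null distribution at 9 versus 3.** There are C(12,3) = 220 equally likely orderings. The numbers giving U = 0, 1, 2, 3, 4, 5 are 1, 1, 2, 3, 4, 5. Hence:

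- P(U ≤ 3) = 7/220 = 0.0318
- P(U ≤ 4) = 11/220 = 0.0500 exactly
- P(U ≤ 5) = 16/220 = 0.0727

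**Normal approximation at 9 versus 3.** The mean is 27/2 = 13.5 and the SD is √(3 × 9 × 13/12) = √29.25 = 5.41.

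- U = 4, uncorrected: z = (4 − 13.5)/5.41 = −1.76, p = 0.0395
- U = 4, continuity-corrected: z = (4.5 − 13.5)/5.41 = −1.66, p = 0.0480
- U = 5: p = 0.058 uncorrected and 0.070 corrected

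Both forms reject at U = 4 and not at U = 5, even with a strict inequality.

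**Power at the planned effect.** The shift is 0.82/0.436 = 1.881 SD, and 10^0.82 = 6.6. Simulation of 2,000,000 normal samples gives:

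| Rule at 9 versus 3 | Rejects when | True size | Power |
|---|---|---|---|
| Exact p ≤ 0.05 | U ≤ 4 | 5.0% | 80.0% |
| Normal approximation p < 0.05, either form | U ≤ 4 | 5.0% | 80.0% |
| Exact p < 0.05, read strictly | U ≤ 3 | 3.2% | 71.8% |

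The first two rows reproduce the plan's 80%. The gap is 80.0 − 71.8 = 8.2 points, the probability that U = 4 under the planned effect. Under the null that probability is 4/220 = 1.8%. Under the strict exact rule, 80% power would need about 0.91 log10 (8.2-fold).

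**With no losses, 10 versus 4.** There are C(14,4) = 1001 orderings.

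- P(U ≤ 7) = 38/1001 = 0.038 and P(U ≤ 8) = 53/1001 = 0.053. The exact test therefore rejects at U ≤ 7 whether the rule is < or ≤, with power 85.3%.
- The uncorrected approximation has mean 20 and SD √(4 × 10 × 15/12) = 7.07. At U = 8, z = −12/7.07 = −1.70 and p = 0.045, so it rejects. Its true size is 5.3% and its power 89.3%.
- The corrected approximation gives p = 0.052 at U = 8 and agrees with the exact test.

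**Other splits.** At 10v3, 9v4, 8v4, 8v3, 7v3, 10v2, 9v2 and 8v2, no attainable exact p-value equals 0.05. Among the ten splits checked, < and ≤ differ only at 9 versus 3.

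**The case for a change.** The best case for a change is this. 9 versus 3 is the size on which the protocol rests its power. The exact test is a natural choice with three comparators, and section 14.4.3 does print a strict inequality. The plan sets a formal threshold for a co-primary endpoint, so calling it a pilot does not excuse an undefined decision. Under the planned effect there is about an 8% chance of the one result on which the readings differ. Nor is the open choice of method confined to that split: at 10 versus 4, U = 8 rejects under the uncorrected approximation and under neither of the others. One sentence would settle it.

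The arithmetic stands, and so does the observation that the p-value method is not named. The step from there to a wrong figure or a contradiction does not stand. A test at level 0.05 may reject at U ≤ 4, whose size is exactly 0.05, and p < 0.05 is everyday shorthand for testing at that level. The two sections conflict only if the reader supplies an exact test and also takes the inequality literally at a tie. That strict reading is conservative (3.2%), so it cannot add false positives. The 10 versus 4 example is a separate matter of approximation error: it involves no conflict between the sections, moves the true size only to 5.3%, and concerns a result with 89.3 − 85.3 = 4.0% probability under the planned effect. Nothing in the documents suggests that the method would be picked to suit the result.

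**Conclusion.** No change to the plan is needed. The 80% in section 14.3 is correct for the one-sided level-0.05 test at 9 versus 3, and it agrees with section 14.4.3 under both normal approximations and under the exact test with p ≤ 0.05. The 71.8% arises only with an exact p-value, a strict inequality and exactly 9 versus 3 evaluable. The conclusion then changes only if U is exactly 4. Those evaluable numbers are an allowance for losses from 10 versus 4, and section 7.4 replaces stage 3 participants who drop out before the first dose. With no losses the exact test has 85.3% power under either reading.

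What remains is a missing detail that a trial statistician fills without harm. At the two sizes considered, the candidate methods have true size from 3.2% to 5.3%. In an exploratory pilot whose power statement already sets multiplicity aside, an 8-point difference in one scenario changes no enrolment number, visit or stopping decision.

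This rests on the plan's own SD of 0.436, normally distributed changes, no ties, and a single pairwise comparison of the combination with one single-agent arm.

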## **4.0 STUDY OBJECTIVES**

### **4.1 Primary Objectives**

- 4.1.1 To evaluate the safety and tolerability of combined treatment with panobinostat and PEG-IFN- $\alpha$ 2a in individuals with well-controlled HIV-1 infection on suppressive cART.
- 4.1.2 To evaluate effects of combined treatment with panobinostat and PEG-IFN- $\alpha$ 2a on the reservoir of HIV-1 infected cells in comparison to effects of treatment with panobinostat alone. For this primary efficacy objective, the reservoir measurements will be CD4 T cell-associated proviral HIV-1 DNA levels.

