## **6.0 STUDY DESIGN**

This study will be a prospective, randomized, open-label, dose-escalation exploratory clinical trial with the primary objective to evaluate the safety of combined treatment with the HDACi panobinostat and pegylated Interferon- $\alpha$ 2a, and to assess the efficacy of the combined treatment regimen to reduce the reservoir of HIV-1 infected cells in comparison to treatment with panobinostat as a single agent. Sequential cohorts with increasing doses of panobinostat will be enrolled. The first two dosing cohorts (stages 1 and 2) will serve primarily to assess the safety of panobinostat administration together with pegylated IFN- $\alpha$ 2a; the third dose cohort (stage 3) has a larger sample size to allow for comparison of the effects of panobinostat plus pegylated IFN- $\alpha$ 2a versus panobinostat or pegylated IFN- $\alpha$ 2a alone on the HIV reservoir. The clinical trial will involve a collaboration of three institutions: the Division of Infectious Diseases at Massachusetts General Hospital in Boston, MA, the Division of Infectious Diseases at the Brigham and Women's Hospital in Boston, and the Novartis Institute of Biomedical Research in Cambridge. The clinical trial will be conducted in the Infectious Diseases Clinical Trials Unit (CTU) at the Massachusetts General Hospital.

Participants must have HIV-1 RNA levels <50 copies/mL for at least two years, must have been on suppressive antiretroviral therapy for at least 2 years, must have a CD4 T cell count >400 cells/mm^3 at study screening, and must have been on a stable and acceptable ART regimen for at least 12 weeks prior to screening. An acceptable regimen includes 2 NRTIs with either one NNRTI (efavirenz or rilpivirine) or a non-boosted integrase inhibitor (raltegravir or dolutegravir). Patients who started treatment during early disease (within <12 months after transmission) and patients who started treatment in chronic infection ( $\geq$  12 months after HIV-1 transmission) are eligible to participate.

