### 7.5 Randomization

Participants will be randomized to treatment Arm A or treatment Arm B or treatment Arm C (in stage 3 only). Participants in treatment Arm A (n=2 participants in stage 1 and 2; n=4 participants in stage 3) will receive treatment with panobinostat only, and participants in treatment Arm B (n=6 participants in stage 1 and 2; n=10 participants in stage 3) will receive combined treatment with panobinostat and pegylated IFN- $\alpha$ 2a. Participants in Arm C (n=4 in stage 3) will receive treatment with pegylated IFN- $\alpha$ 2a only.

Randomization will occur on day 0 of the study, prior to administration of the first dose of the study medication. Participants will be informed about the randomization decision, and open-label study medication will be administered.

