### 10.8 Contraindications to further administration of study drugs

Clinical events listed below constitute absolute **contraindications to further administration** of the study medication; if any of these events occur during the study, the participant must not receive additional doses of the investigational product but may continue other study procedures at the discretion of the investigators. The participant must be followed until resolution of the event, as with any adverse event.

- Early or delayed hypersensitivity reactions
- Pregnancy

The following adverse events constitute **contraindications to administration** of the study medication **at that point in time**; if any one of these adverse events occurs at the time scheduled for administration of the study drugs, administration of study drugs will be delayed for a maximum of one week or withdrawn from study participation at the discretion of the investigators. The participant must be followed until resolution of the event, as with any adverse event (see Section 10.7).

- Acute disease, defined as the presence of a moderate or severe illness with or without fever. However, study medication can be administered to persons with a minor illness such as diarrhea, mild upper respiratory infection with or without low-grade febrile illness, i.e. oral temperature < 100.5F.
- Oral temperature of  $\geq 100.5F$

### 10.9 Criteria for Study Continuation to stage 2 and 3

After completion of stage 1, all safety data will be reviewed by the internal safety review committee (ISRC), the external safety monitoring committee, the IRB and the FDA. The study can only proceed to stage 2 if all of these committees agree that the safety profile in stage 1 is acceptable. A similar interim review will occur after completion of stage 2 to determine study progression to stage 3.

Dose escalation criteria are defined as:

- a) No more than one subject has experienced a  $\geq$  Grade 3 toxicity event that is related to study treatment (as judged by the investigators) prior to or on Day 28 after the treatment administration; however, if

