## 14.0 DATA EVALUATION AND STATISTICAL ANALYSIS

### 14.1 Co-primary Endpoints

- The cumulative frequency and severity of grade  $\geq 1$  adverse events, grade  $\geq 1$  laboratory abnormality, and other serious adverse events (SAEs) during the one week treatment period.
- Changes from baseline in the reservoir of HIV-1 infected CD4 T cells, measured on a log scale using assays to evaluate CD4 T cell-associated proviral HIV-1 DNA, after completion of the combined treatment (on day 10 after study initiation) in treatment arm A vs. treatment arm B vs. treatment arm C.

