## Protocol

absolute and relative number of participants experiencing at least 1 event, the total number of events, the type of events, and the causality assessment. Due to the low expected safety event rates (based on the prior clinical study with panobinostat in HIV-1 participants), the study is not powered to do a formal statistical comparison between the randomized arms. AE rates will be presented for descriptive purposes.

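### Should Tables 7 and 8 give safety detection probabilities for the combination arm instead of for all arms pooled?

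*Combined protocol and SAP*

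**What the plan says.** The first primary objective in Section 4.1 is "To evaluate the safety and tolerability of combined treatment with panobinostat" and PEG-IFN-α2a. Section 6.0 adds a purpose for the early stages: "The first two dosing cohorts (stages 1 and 2) will serve primarily to assess the safety of panobinostat administration together with pegylated" interferon. Only Arm B receives both drugs. Section 7.5 gives its size: "participants in treatment Arm B (n=6 participants in stage 1 and 2; n=10 participants in stage 3". The remaining participants are on panobinostat alone (2, 2 and 4 in stages 1, 2 and 3) or, in stage 3 only, on interferon alone (4).

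Section 14.3 introduces Tables 7 and 8 by saying that they "display the probability of observing at least one or two participants with primary safety event with n=8 and 18 receiving study treatment". The columns are headed N=8 and N=18, the rows run from a true probability of 0.01 to 0.20, and the text picks out the 10% row: above 57% for stages 1 and 2, and 85% for stage 3.

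The safety endpoint in Section 14.1 covers grade 1 or higher adverse events, grade 1 or higher "laboratory abnormality, and other serious adverse events (SAEs) during the one week treatment period". It names no arm. On analysis, Section 14.4.2 says that the study is not powered for a formal comparison of arms and that "AE rates will be presented for descriptive purposes". Section 14.4.3 says: "Primary safety endpoints will be tabulated by Cohorts and randomized treatments".

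**The concern.** The objective concerns the combination, but the tables describe everyone treated in a stage. Of the 8 participants in stage 1 or 2, two never receive interferon. Of the 18 in stage 3, eight (44%) receive only one of the two drugs. The pooled figure equals the chance of seeing a toxicity of the combination only if the single-agent arms share its event rate, and the combination's safety is the open question.

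A reader who takes 57% and 85% as sensitivity for the combination would credit the trial with more than it has. An event-free cohort could be over-read in the same way, by setting zero events against 8 or 18 participants when 6 or 10 received the combination.

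There is a second, smaller oddity. The tables speak of the primary safety event, which Section 14.1 defines at grade 1 or higher, yet their rates stop at 20%. That range looks low for an any-grade endpoint.

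**Working it through.** **Inputs.** Stage totals 8, 8 and 18 (Sections 3.0 and 14.3). Arm B sizes 6, 6 and 10 (Section 7.5). True rates p of 0.01 to 0.20 (Tables 7 and 8).

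**Formulas.** With n participants and a common rate p:
- P(at least 1) = 1 − (1−p)^n
- P(at least 2) = 1 − (1−p)^n − n·p·(1−p)^(n−1)

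**The plan's own figures at p = 0.10.**
- n=8: 1 − 0.9^8 = 1 − 0.4305 = 0.5695 (printed 0.57). At least two: 0.5695 − 0.8 × 0.9^7 = 0.5695 − 0.3826 = 0.187 (printed 0.19).
- n=18: 1 − 0.9^18 = 1 − 0.1501 = 0.8499 (printed 0.85). At least two: 0.8499 − 1.8 × 0.9^17 = 0.8499 − 0.3002 = 0.550 (printed 0.55).

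The other 20 cells also reproduce to two decimals. The text's claim of more than 57% is a rounding slip, since the exact value is 56.95%.

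**Arm B at p = 0.10.**
- n=6: 1 − 0.9^6 = 1 − 0.5314 = 0.469. At least two: 0.469 − 0.6 × 0.9^5 = 0.469 − 0.354 = 0.114.
- n=10: 1 − 0.9^10 = 1 − 0.3487 = 0.651. At least two: 0.651 − 1.0 × 0.9^9 = 0.651 − 0.387 = 0.264.

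P(at least 1) across the tabulated rates:

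| True rate | n=6 | n=8 | n=10 | n=18 |
|---|---|---|---|---|
| 0.01 | 0.06 | 0.08 | 0.10 | 0.17 |
| 0.05 | 0.26 | 0.34 | 0.40 | 0.60 |
| 0.10 | 0.47 | 0.57 | 0.65 | 0.85 |
| 0.12 | 0.54 | 0.64 | 0.72 | 0.90 |
| 0.15 | 0.62 | 0.73 | 0.80 | 0.95 |
| 0.20 | 0.74 | 0.83 | 0.89 | 0.98 |

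**Zero events observed.** The one-sided 95% upper limit, 1 − 0.05^(1/n), is 39% for n=6 against 31% for n=8, and 26% for n=10 against 15% for n=18.

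**Where a count drives a decision.**
- Section 10.9 allows escalation if "No more than one subject has experienced a" related toxicity of grade 3 or higher and none has a related one of grade 4 or higher. It counts subjects without naming an arm, so the stage total of 8 is the relevant n. The columns for at least one and at least two events match those two limits in form.
- Sections 12.2 and 12.3 suspend dosing on one, or two or more, participants with a related grade 4 event, again in any arm.
- All eight participants in stages 1 and 2 take panobinostat, the only drug whose dose is escalated.

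**The any-grade reading.** The documents give no one-week rate for this regimen, so rates of 40% and 60% are assumptions. At 40%, P(at least 1) is 1 − 0.6^6 = 95% for n=6 and 1 − 0.6^8 = 98% for n=8. At 60% it is 99.6% and 99.9%. If the event is that common, the choice between 6 and 8 hardly matters. The gap of 10 to 20 points arises for rarer events, such as the higher grades that the escalation and suspension rules count.

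**The case for a change.** The strongest case for acting is that safety is descriptive. With no formal comparison and no planned intervals, the detection probabilities are the plan's only quantitative statement of what the trial can show on its first co-primary endpoint, and they are given for an n that is not the combination's. In stage 3 the chance of at least two events falls from 55% to 26%, less than half, and adding columns would cost almost nothing.

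The arithmetic stands, and so does the observation that no sentence gives a figure for n=6 or n=10. The consequence does not follow. The column headings state their n, and the introductory sentence describes it as those on study treatment. Nothing is offered as an Arm B probability, and a misreading requires ignoring the label. Results by cohort and arm will carry denominators of 6, 6 and 10, from which an analyst would attach exact intervals as a matter of course (12% to 88% for 3 of 6, for example) without an amendment.

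The point about the 1–20% range also has some force. Section 5.4.3.1 reports 15 likely related grade 1 events in the earlier single-group panobinostat trial of 15 participants, over a longer course, while Section 14.4.2 cites that trial as grounds for expecting low rates. This is loose wording about which events the tables illustrate. It alters no analysis.

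**Conclusion.** No change is called for. Tables 7 and 8 are correct for what they label, and the all-arm n suits the rules that act on safety counts. For the combination alone the figures at a 10% rate are lower: 47% against 57% for at least one event in each of stages 1 and 2, and 65% against 85% in stage 3. Anyone interpreting an event-free Arm B should use those figures. They assume independent participants, a common rate within the arm and the planned arm sizes. Replacement of dropouts under Section 7.4 could raise the number exposed slightly.

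Printing the Arm B columns, naming the severity and relatedness that the 1–20% range describes, or writing 57% without the inequality sign would be optional tidying. None of these would alter enrolment, escalation, suspension, a test or a conclusion. An analyst following Sections 14.4.2 and 14.4.3 as written already reports the combination on its own denominators.
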